14.4 Sample Size Adequacy

Power analyses were conducted for detectable mean changes from baseline (conservatively) assuming a within subject correlation of $r=0.70$. For between group differences, assuming 10% loss to follow up from all causes (mortality, attrition, etc.) by 16 weeks post randomization (CAP n=105 in the PUSH arm and this study will have n=30, so effective n=94 compared to n=27 including attrition). The study will have 80% power to detect differences of 0.475 standard deviations assuming two-sided tests and an alpha level of 0.05. These differences are considered small-to-moderate effects using Cohen's criteria for interpretation of effect sizes (where 0.2 is "small" and 0.5 is "medium"). Given a 6MWT mean of 186.7 and SD=55.8 in the most recent overall sample from CAP (n=199, DSMB report May 2017), this would translate into a difference of 22.9. Similar magnitude of effects (SD=0.41) are detectable comparing to other measures available in the CAP study (e.g, SPPB, 3MS, etc.).

For outcomes only available in the CAP-MP study, the comparison sample is 19 subjects in CAP-MP PUSH. Assuming 10% loss to follow up (n=17 in CAP-MP PUSH group vs n=27 in pilot study), the study will have 80% power to detect between group differences of 0.62 standard deviations assuming two-sided tests and an alpha level of 0.05. This is considered a moderate-to-large effect size by Cohen.

Section 15: Data Capture, Data Management, and Quality Assurance

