## **Sample Size Adequacy**

Power analyses were conducted for detectable mean changes from baseline (conservatively) assuming a within subject correlation of  $r=0.70$ . For between group differences, assuming 10% loss to follow up from all causes (mortality, attrition, etc.) by 16 weeks post randomization (CAP n=105 in the PUSH arm and this study will have n=30, so effective n=94 compared to n=27 including attrition). The study will have 80% power to detect differences of 0.475 standard deviations assuming two-sided tests and an alpha level of 0.05. These differences are considered small-to-moderate effects using Cohen's criteria for interpretation of effect sizes (where 0.2 is "small" and 0.5 is "medium"). Given a 6MWT mean of 186.7 and SD=55.8 in the most recent overall sample from CAP (n=199, DSMB report May 2017), this would translate into

a difference of 22.9. Similar magnitude of effects ( $SD=0.41$ ) are detectable comparing to other measures available in the CAP study (e.g, SPPB, 3MS, etc.).

For outcomes only available in the CAP-MP study, the comparison sample is 19 subjects in CAP-MP PUSH. Assuming 10% loss to follow up (n=17 in CAP-MP PUSH group vs n=27 in pilot study), the study will have 80% power to detect between group differences of 0.62 standard deviations assuming two-sided tests and an alpha level of 0.05. This is considered a moderate-to-large effect size by Cohen.

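### The primary detectable difference of 22.9 m does not follow from 0.475 SD and an SD of 55.8 m, which give 26.5 m; under the stated inputs, power at 22.9 m is about 67-68%, not 80%

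*Protocol*

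**What the plan says.** Protocol section 14.4 bases its power analyses on change from baseline with a within-subject correlation of 0.70, which it calls conservative. It allows 10% loss to follow-up, which takes 105 CAP PUSH participants and 30 pilot participants to 94 and 27. On that basis it states: "The study will have 80% power to detect differences of 0.475 standard deviations assuming two-sided tests and an alpha level of 0.05".

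It then moves to the scale of the six-minute walk: "Given a 6MWT mean of 186.7 and SD=55.8 in the most recent overall sample from CAP", and "this would translate into a difference of 22.9". No unit is printed; metres is the only sensible reading. The next sentence turns to the remaining CAP outcomes: "Similar magnitude of effects (SD=0.41) are detectable comparing to other measures available in the CAP study".

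The SAP repeats the paragraph under Sample Size Adequacy, including "a difference of 22.9". The planned model (protocol 14.2 and SAP, Secondary Objectives) takes the group-by-time coefficient b3 as the treatment effect, that is, the between-group difference in mean change from baseline to 4 months.

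**The concern.** The standardised effect, the SD and the distance are printed together and do not agree. If 0.475 SD is what the study can detect and the SD is 55.8 m, the distance is 26.5 m. The printed 22.9 m corresponds to 0.41 SD, the value that appears in the next sentence for other outcomes. This suggests that results from two different calculations were mixed.

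The 22.9 figure is the only statement, on the outcome's own scale, of what the primary comparison can detect, and it errs in the favourable direction. A reader who trusts it would take a null result as reasonable evidence against a benefit of about 23 m, when under the plan's own assumptions the study has a materially lower chance of finding one. The pilot is also meant to inform the size of a definitive study (protocol section 1), so its statement of sensitivity should be right.

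**Working it through.** **Inputs, all from protocol 14.4 unless noted**

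- Two-sided alpha 0.05, power 80%: multiplier 1.960 + 0.842 = 2.802
- Within-subject correlation r = 0.70
- Evaluable participants: 94 (CAP PUSH) and 27 (PUSH Plus Protein)
- SD of the six-minute walk: 55.8 m
- Contrast: difference in mean change (b3, section 14.2)

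**Step 1. Reproduce the plan's 0.475 SD.** For a change score, the SD of change in units of the raw SD is √(2(1 − r)).

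- √(2 × 0.30) = 0.7746
- √(1/94 + 1/27) = 0.2183
- Detectable difference = 2.802 × 0.7746 × 0.2183 = 0.474 SD (0.478 SD with the t distribution)

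The stated 0.475 is confirmed. Power at 0.475 SD is 80.2% (normal) or 79.6% (noncentral t).

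**Step 2. Convert to metres.**

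- 0.475 × 55.8 = 26.5 m
- Directly from step 1: 0.474 × 55.8 = 26.4 m, or 0.478 × 55.8 = 26.7 m with t
- Working back from the printed figure: 22.9 / 55.8 = 0.410 SD
- For 22.9 m to equal 0.475 SD, the SD would have to be 22.9 / 0.475 = 48.2 m, which appears in neither document

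The understatement is (26.5 − 22.9) / 26.5 = 13.6%.

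**Step 3. Power at 22.9 m under the stated inputs.**

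- Standard error = 55.8 × 0.7746 × 0.2183 = 9.44 m
- 22.9 / 9.44 = 2.43
- Power = Φ(2.43 − 1.96) = 68.0% (normal), or 67.3% with the noncentral t

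With 94 comparators fixed, 80% power at 22.9 m would need about 40 evaluable pilot participants rather than 27.

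**Step 4. The 0.41 SD for other CAP measures.** These outcomes are compared with the same CAP group, and 14.4 gives no different n or r for them. Since 0.41 × 55.8 = 22.9, this is the same standardised effect as in step 3, so power is again 67-68%; 80% power needs about 0.475-0.48 SD.

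**Step 5. What inputs would give 22.9 m?**

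| Basis | n | r | Detectable SD | Metres |
|---|---|---|---|---|
| Change score, as stated | 94 vs 27 | 0.70 | 0.474 | 26.4 |
| Baseline-adjusted (ANCOVA) | 94 vs 27 | 0.70 | 0.437 | 24.4 |
| Change score, no attrition | 105 vs 30 | 0.70 | 0.449 | 25.1 |
| ANCOVA, no attrition | 105 vs 30 | 0.70 | 0.414 | 23.1 |
| Change score | 94 vs 27 | about 0.775 | 0.410 | 22.9 |
| Change score, no attrition | 105 vs 30 | 0.75 | 0.410 | 22.9 |

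Every row at or near 22.9 m departs from the stated correlation or the stated group sizes.

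**The case against.** The multiplication cannot be defended, but four points can fairly be made about what is built on it.

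First, the 67-68% depends on r = 0.70, which the plan chose as conservative. Section 14.1 reports r = 0.78 for usual walking speed (13 participants) and above 0.80 for various physiologic measures. With 94 versus 27 and a change score, power at 22.9 m is about 81% at r = 0.78 and 84% at r = 0.80 (normal approximation). With ANCOVA at r = 0.70 it is 74-75%. This stands as a condition on the power figure. It does not rescue the text: 0.70 is the only correlation that 14.4 states for its power analyses, and a higher one would make the printed 0.475 SD wrong instead.

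Second, the section may not rest on one method throughout. Its 0.62 SD for the CAP-MP comparison (17 versus 27) matches ANCOVA at r = 0.70 (0.6195), not a change score (0.672). So the origin of the 22.9 and 0.41 pair cannot be settled from the documents. However, ANCOVA at the stated r and n gives 0.437 SD and 24.4 m for the primary comparison, which matches none of the printed figures.

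Third, replacing 0.41 with 0.475 assumes that r = 0.70 also applies to the other CAP measures. The section's opening sentence supports that reading, but the sponsor may have used measure-specific correlations, which would then have to be stated.

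Fourth, this is a pilot of fixed size. The error changes no estimand, model, alpha level or procedure, and both 22.9 m and 26.5 m are roughly half of the 50 m change that section 9.4 treats as clinically meaningful. That is fair, and it limits the consequence to how the study's sensitivity is described and how a null result is read.

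**Conclusion.** The concern holds. That 0.475 SD with an SD of 55.8 m is 26.5 m and not 22.9 m is arithmetic and depends on no modelling choice; nothing else in the protocol or SAP reconciles the two. Because 0.475 reproduces from the section's stated inputs, the metre figure is the one that does not fit. The stated detectable difference is too favourable by about 14%. Power at 22.9 m, and likewise at 0.41 SD for the other CAP measures, is 67-68% given r = 0.70, 94 versus 27 evaluable participants, two-sided alpha 0.05 and a change-score contrast. It would be higher under a stronger correlation or baseline adjustment, but the section claims neither. The correction is to the text, not to the design.

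**What to change.** In protocol 14.4 and in the SAP's Sample Size Adequacy section:

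- Replace the difference of 22.9 with 26.5 m, and print the unit.
- Replace the 0.41 SD for the other CAP measures with 0.475 SD (same n, same r). If a different correlation was used for them, state it and show the resulting effect size.
- Alternatively, keep 22.9 m and give its power as about 67% at r = 0.70.

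If the sponsor in fact used another correlation or a baseline-adjusted analysis, the section should say so and the 0.475 SD should be recomputed on that basis, so that all the figures come from one calculation.

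The cost is two numbers in each document and a slightly less favourable statement of sensitivity. No additional participants are needed.

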14.2 Secondary Objectives

A longitudinal analysis using Generalized Estimating Equations (GEEs) will be employed. A model of the form $Y(t) = a + b_1 X + b_2 t_4 + b_3 X t_4$ will be used where: $Y(t)$ is the dependent variable Y at time t (which is 0 or 4 months post baseline testing); a is the intercept; X is an indicator variable for treatment group (PUSH vs PUSH+ Protein); t_4 is an indicator variable for time at 4 months post baseline testing; $X t_4$ is an interaction term for treatment and time; and b_1 through b_3 are empirically derived regression coefficients. An unstructured covariance matrix, an identity link function, and robust standard errors will be used. The effect of intervention on each mechanistic factor will be assessed by estimating the magnitude of the coefficient b_3 , which is interpreted as mean change in outcome from baseline to 4 months comparing PUSH Plus Protein to PUSH alone. The primary outcome will be the 6-minute walk test (6MWT). Other potential outcomes include: activities of daily living (ADLs), quality of life, lower-extremity physical performance, increase of ≥ 50 meters in distance walked in six minutes, cognitive status, and nutritional status.

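### With the plan's own change model and r = 0.70, the CAP-MP comparison (17 vs 27) has 80% power for 0.67–0.69 SD, not 0.62 SD; power at 0.62 SD is about 71–73%

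*Protocol*

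**What the plan says.** Protocol section 14.4, repeated in the SAP under Sample Size Adequacy, makes two power statements.

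- **CAP comparison, 94 versus 27 after loss:** "The study will have 80% power to detect differences of 0.475 standard deviations assuming two-sided tests and an alpha level of 0.05".
- **CAP-MP comparison:** "the comparison sample is 19 subjects in CAP-MP PUSH", which becomes 17 after loss: "Assuming 10% loss to follow up (n=17 in CAP-MP PUSH group vs n=27 in pilot study". For these numbers, "the study will have 80% power to detect between group differences of 0.62 standard deviations assuming two-sided tests and an alpha level of 0.05".

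The section opens by saying that the power calculations concern mean change from baseline with a within-subject correlation of 0.70, which it calls conservative. It gives no other correlation for the CAP-MP paragraph.

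Section 14.2 sets the analysis: a GEE with terms for group, time and group by time. "The effect of intervention on each mechanistic factor will be assessed by estimating the magnitude of the coefficient" of the interaction term, b3. The section goes on to describe that term as one "which is interpreted as mean change in outcome from baseline to 4 months comparing PUSH Plus Protein to PUSH alone". Neither document names a model that adjusts the follow-up value for baseline.

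**The concern.** Both figures sit in one section, under one stated correlation and one stated type of effect, so one formula should give both. It does not: the formula that yields 0.475 SD yields a value well above 0.62 SD when the CAP-MP sample sizes are put in.

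The 0.62 SD is the only power statement for outcomes available only in CAP-MP. The Executive Summary lists the mechanistic aims that draw on that study: thigh muscle volume and attenuation, lower-extremity strength, gait parameters, bone density and strength, bone turnover and inflammatory cytokines. If power is overstated, null findings on these outcomes will look more informative than they are. The pilot is also meant to inform the size of a definitive study, and an unexplained mix of variance formulas is a poor starting point for that.

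**Working it through.** **Inputs**

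- Two-sided alpha 0.05 and 80% power (section 14.4): 1.960 + 0.842 = 2.802.
- Group sizes 17 and 27 for CAP-MP, 94 and 27 for CAP (section 14.4).
- Within-subject correlation r = 0.70 (section 14.4).
- Estimate b3, the between-group difference in mean change (section 14.2).
- Scale: SD of the outcome itself. Section 14.4 converts to metres with the 6MWT SD of 55.8; I assume the same scale for CAP-MP outcomes, and equal variance at both times and in both groups.

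**Formula**

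Detectable difference (in SD) = 2.802 × f × √(1/n₁ + 1/n₂), where

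- change score (b3): f = √(2(1 − r)) = √0.60 = 0.7746
- ANCOVA: f = √(1 − r²) = √0.51 = 0.7141

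b3 takes the change-score factor because the model fits a separate baseline mean for each group.

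**Step 1: reproduce the CAP figure (stated 0.475 SD).** √(1/94 + 1/27) = 0.2183.

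- Change score: 2.802 × 0.7746 × 0.2183 = 0.474 (0.478 with the t distribution). This matches.
- ANCOVA: 2.802 × 0.7141 × 0.2183 = 0.437 (0.440 with t). This does not.

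**Step 2: apply the same method to CAP-MP (stated 0.62 SD).** √(1/17 + 1/27) = 0.3096, and 2.802 × 0.3096 = 0.867.

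| Variance factor, r = 0.70 | Normal | t | Power at 0.62 SD (normal / t) |
|---|---|---|---|
| Change score (b3, as planned) | 0.672 | 0.688 | 73.4% / 71.4% |
| ANCOVA (not planned) | 0.620 | 0.634 | 80.1% / 78.2% |

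Power under b3: 0.62 / (0.7746 × 0.3096) = 2.585; 2.585 − 1.960 = 0.625; Φ(0.625) = 0.734. The noncentral t gives 0.714.

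**Step 3: can another reading rescue 0.62 under the change model?**

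- No dropout (19 vs 30), r = 0.70: 0.636 SD (normal) or 0.650 SD (t).
- All baselines used (19 and 30) with follow-up on 17 and 27: 0.667 SD, with 74.1% power at 0.62 SD.
- One-sided test: 0.596 or 0.606 SD, but the plan says two-sided.
- Correlation needed to get 0.62 SD: 0.745 (normal) or 0.756 (t). The correlation that gives 0.475 SD for 94 versus 27 is 0.70.

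So no single formula with a single correlation gives both figures.

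**Step 4: size of the gap.** 0.672 / 0.62 = 1.08 and 0.688 / 0.62 = 1.11, so the detectable difference is 8% to 11% larger than stated. Keeping 80% power at 0.62 SD under b3 would need about 20 comparison participants with follow-up at the same 27:17 ratio (normal approximation). CAP-MP is complete and supplies 19 before loss.

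**The case against.** The best defence has four parts.

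1. **0.62 is not a slip.** It is the standard ANCOVA result at the plan's own r. That is true and probably explains the number, but it identifies the cause without removing the mismatch: the planned estimate is b3, and the same formula contradicts the 0.475 SD in the preceding paragraph.

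2. **0.475 is not a secure anchor.** Section 14.4 converts the detectable effect to 22.9 m, and 22.9 / 55.8 = 0.41 SD, whereas 0.475 × 55.8 = 26.5 m. ANCOVA with 105 versus 30 and no loss gives 0.414 SD, so one formula might lie behind both 0.41 and 0.62. That is possible but not shown; a change score with r of about 0.775 at 94 versus 27 also gives 0.41. The point stands as a reason to reconcile the whole section. It does not make 0.62 correct for b3, which follows from section 14.2 whatever 0.475 means.

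3. **The true correlation may be higher.** Section 14.1 reports 0.78 for usual walking speed in 13 CAP-MP participants and more than 0.80 for physiologic measures in other data. Under the change model, power at 0.62 SD is 80.8% (normal) or 79.0% (t) at r = 0.75, and 85.5% or 83.9% at r = 0.78. So actual power is uncertain, not shown to be below 80%. But the plan chose 0.70 as its basis, and one walking-speed estimate from 13 people need not hold for CT, bone markers or cytokines.

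4. **The stakes are small.** These are secondary outcomes of a 30-patient pilot, no decision rule uses 0.62, the primary comparison is untouched, and results will be read from the estimate of b3 and its precision. This is fair and limits the importance of the point.

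**Conclusion.** The concern holds. At r = 0.70, two-sided alpha 0.05 and 17 versus 27, the planned b3 analysis has 80% power for 0.67 SD (normal) to 0.69 SD (t). At 0.62 SD its power is 73% or 71%, a shortfall of 7 to 9 percentage points.

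The conclusion is conditional on the plan's stated correlation and on b3 as written; a correlation of about 0.75 or a pre-specified baseline-adjusted analysis would bring the claim close to true. The statement needs correcting because it does not follow from the plan's own model, but a gap of 0.05 to 0.07 SD on a pilot's secondary outcomes is modest in practice. The calculation also assumes follow-up on all 17 and 27. Section 10.1 does not mark the serologic blood draw, hip DXA, GAITrite or Biodex as required at baseline, so numbers for those outcomes could be lower.

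**What to change.** In Protocol section 14.4 and the SAP's Sample Size Adequacy section, take one of these courses:

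- **Restate the effect:** 80% power to detect 0.69 SD (t-based; 0.67 SD by normal approximation) for 17 versus 27, r = 0.70, under the b3 analysis.
- **Restate the power:** keep 0.62 SD and give power as about 71% (t) or 73% (normal).
- **Change the analysis:** pre-specify a baseline-adjusted model for the CAP-MP outcomes and say that 0.62 SD rests on it (0.634 SD with t). This is more than a wording change, because in a non-randomised comparison adjusting for baseline alters what is estimated. It would also have to be squared with 0.475 SD, which rests on the change score.

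In every case, state the variance formula and correlation behind each figure and use the same ones for both comparisons. Reconcile 0.475 SD with 22.9 m and 0.41 SD in the same edit.

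The first two courses cost one slightly less favourable number in each document. None needs extra participants or procedures.

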15.1 Data Management

15.1.1 Processing of Paper Data Forms

Field staff will bring in data forms within 1 week of the visit and place them in the appropriate tray in the study office. Office staff will review each form for completeness and check any required fields. Submitted data forms will be tracked in an Access® database. Forms are then double entered into the appropriate data entry database and filed in the participant binder.

15.1.2 Reportable Adverse Events Coding

RAEs will be coded using MedDRA (version 15.1, release date September 1, 2012). The MedDRA coding dictionary is integrated with the study database.

15.1.3 Extraction of Data for Analysis and Reporting

Data will be extracted using StatTransfer and converted to SAS data sets for analysis and reporting. Where required, data will be merged and recoded using validated SAS code to create “analysis data sets”. Specifications for these analysis data sets will be drafted and updated as needed.

15.2 Protection of Data

15.2.1 Physical Security and Backup

All tracking and data entry databases are password protected with limited access. Each are stored on the School of Medicine’s secure server. The server is backed up daily. SAS programs and datasets are also stored on the server and backed up daily.

15.3 Study Management Database

An Access® database will be used to track study visits, generate schedules of future study visits, status of participants, activities of study staff members, form completion, and form submission. The database will provide a standard way to track time-sensitive study activities throughout the study. The study management database will be password-protected and saved on the server that will be automatically backed up daily. Access to the database will be restricted to office staff. There will be several standard reports available in the database to use for a variety of tracking issues. Additional reports will be created as needed. Data for the tracking database will come from tracking forms completed by study staff.

15.4 Quality Assurance (QA)

Quality assurance (QA) will be a shared responsibility of all study personnel. The goal of QA monitoring will be to track study progress and develop the information necessary to ensure: 1) enrollment of the required number of participants; 2) adherence to treatment protocol; 3) that data are reported completely, verifiably and in a timely fashion; and 4) participant safety, by accounting for expected AEs and RAEs. Study monitoring will be based on early implementation of reviews of accumulating data with rapid feedback to the PI regarding problem areas. The Investigative team will regularly review progress.

15.4.1 Training

Staff will be trained at the initial training session(s). Certification and recertification will be required in order to assure that staff have a clear understanding of the study protocol and Manual of Procedures (MOP). Separate training sessions will be provided for staff conducting study assessments, telephone interviewers, PTs providing the PUSH intervention, staff conducting screening and informed consent procedures, and the registered dieticians. The study coordinator will attend all training sessions.

Training sessions will cover recruitment; obtaining informed consent; collection of protocol-specified data (both questionnaire and performance-based measures); scoring; completion of forms; capturing and reporting expected AEs and RAEs; administering the intervention; performing diet consults; and using the paper-based data forms.

In preparation for training, staff will be asked to read background material (e.g., designated chapters in the MOP). The training session will involve both didactic and interactive components. Training for the different sessions will be provided by investigators with the appropriate expertise. For example, training the PTs to deliver the study interventions will be provided by the IM. Whenever appropriate, trainees will be required to demonstrate acquired

skills. These demonstrations will be observed and critiqued by the trainers and other staff. Trainees will be certified to perform study procedures after successfully completing written and (when appropriate) performance tests.

The study coordinator will be responsible for documenting that certification has been completed.

